8.4. Pharmacokinetic Analyses

The analyses will be carried out on the PK analysis population. All PK parameters will be presented by listings and descriptive summary statistics (mean, SD, median, minimum, maximum geometric mean, and geometric coefficient of variation) separately by group. Individual and mean plasma CBP-307 and moxifloxacin concentration versus time data will be tabulated and plotted by dose level. Graphical displays of PK data may be provided as well.

For each subject, the following PK parameters will be calculated, whenever possible, based on the plasma concentration for CBP-307 and moxifloxacin, according to the model independent approach:

- C_{max}
- t_{max}
- AUC_{0-24}
- AUC_{inf}
- apparent terminal elimination rate constant (λ_z)
- $t_{1/2}$
- apparent total clearance (CL/F)
- apparent volume of distribution during the terminal phase (V_z/F)
- Accumulation ratio (R_{ac}) for C_{max} ($R_{ac[C_{max}]}$) and $R_{ac(AUC_{0-24})}$, calculated as Day 15 C_{max} /Day 7 C_{max} and Day 15 AUC_{0-24} /Day 7 AUC_{0-24} , respectively.

Pharmacokinetic calculations will be performed, if appropriate, using commercial software such as Phoenix® WinNonlin® (Version 8.1 or higher).

Other parameters may be added as appropriate.

Pharmacokinetic analysis will use actual times as recorded on the eCRF. Other data handling procedures will be detailed in the Statistical Analysis Plan.

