7.2.3. Cardiac Telemetry Monitoring

Subjects will be monitored via cardiac telemetry from approximately 1 hour prior to dose administration and until approximately 12 hours postdose on Days 1, 2, 3, and 7 (up-titration days; as described in [Appendix 6](#)). Based on the emerging safety data from the study, the duration of the telemetry may be extended if necessary.

The start and stop date and time of the telemetry monitoring will be recorded in the eCRFs. Clinically significant abnormalities noted from telemetry monitoring will be confirmed by 12-lead ECG if necessary, then after confirming, the abnormalities will be reported as AEs in the eCRF.

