Appendix 3: Total Blood Volume

The following blood volumes will be withdrawn for each subject.

Test	Volume per blood sample (mL)	Maximum number of blood samples	Total amount of blood (mL)
Clinical laboratory evaluations (including serology, syphilis, follicle-stimulating hormone, and serum pregnancy tests)	12.5	5	62.5
CBP-307/Moxifloxacin Pharmacokinetics (includes discard volume per draw)	8	41	328
Total:			390.5

If extra blood samples are required, the maximum blood volume to be withdrawn per subject will not exceed 500 mL.

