3. **Screening and Check-in on Day -2:** Tympanic temperature, respiratory rate, and supine pulse rate and blood pressure. **Other days (except for Days 17, 18, and 19):** Prior to and 2 hours after dosing, supine vital signs (tympanic temperature, pulse rate, respiratory rate, and blood pressure). **Days 17 and 18:** Tympanic temperature, respiratory rate, and supine pulse rate and blood pressure at approximately the same time each day. **Discharge (Day 19):** Prior to discharge, supine vital signs (tympanic temperature, pulse rate, respiratory rate, and blood pressure). **End of Study/Follow-up Visit (Day 29±2 days):** Tympanic temperature, respiratory rate, and supine pulse rate and blood pressure.

4. 12-lead safety ECG will be recorded in triplicates before dosing and in singles 2 hours postdose on all study days (except for Days 17 and 18) and before discharge on Day 19. Postdose safety will be interpreted on-site by the investigator and may be repeated to confirm/refute clinically abnormal findings.
5. Continuous cardiodynamic monitoring (Holter) will be performed for 25 hours on Day -1 (baseline), 1, 6, 15, and 16. The recording will be started at least 1 hour before dosing and at the corresponding clock time on Day -1. Replicate 12-lead ECGs will be extracted from the continuous recording prior to dosing (-30 minutes) and 0.5, 1, 2, 3, 4, 6, 8, 12, and 24 hours postdose on each day. At timepoints for ECG extractions, subjects will be supinely resting in an undisturbed environment. The ECG effects of CBP-307 will be tested on data from Day -1 (baseline for both groups), Day 6 (therapeutic concentrations versus placebo), and Day 15 (supratherapeutic concentrations versus placebo). Assay sensitivity with moxifloxacin will be tested on data from Days -1, 1, 15, and 16.
6. Serum pregnancy test will be performed at screening and urine pregnancy tests will be performed on Day -2 and at the follow-up visit (Day 29±2 days). A positive urine pregnancy test will be confirmed with a serum pregnancy test.
7. Pharmacokinetic samplings will be performed prior to dosing and 0.5, 1, 2, 3, 4, 6, 8, 12, and 24 hours after dosing on each PK sampling day (Days 1, 6, 15, and 16). Additional PK samples will be collected at 72 and 96 hours following dosing on Day 15.

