This will be a Phase I, randomized, double-blind, double-dummy, placebo-controlled, positive-controlled, single-site, 3-arm study to investigate the effects of therapeutic and supratherapeutic oral doses of CBP-307 on the QTc interval in healthy male and female subjects.

Potential subjects will be asked to read and sign an informed consent form (ICF). After informed consent is obtained, screening procedures and tests to establish subject eligibility to enter the study will be performed within 28 days before Day 1. After informed consent has been obtained but prior to the initiation of study treatment administration, only serious adverse events (SAEs) will be reported. After placebo administration to all subjects on Day -1, all adverse events (AEs), whether volunteered, elicited, or noted upon physical examination, will be recorded throughout the study (ie, from Day -1 until the end of the study).

In this study, approximately 64 healthy subjects (at least 30% for each sex) will be randomized into 2 groups (Group 1 and 2) with 32 subjects in each. Group 2 consists of 2 sub-groups (Group 2A and 2B) and each sub-group will be randomized with 16 subjects. Randomized subjects will receive the assigned study drug as a single dose in the morning on

Days 1, 2, 3 to 6, 7 to 15, and on Day 16 (placebo will be administered to all subjects on Day -1).

The following treatments will be administered:

- Starting doses of CBP-307 for titration (0.05 mg on Day 1 followed by an up-titrated dose of 0.1 mg on Day 2)
- A therapeutic dose of CBP-307 (0.2 mg, Days 3 to 6)
- A supratherapeutic dose of CBP-307 (0.5 mg, Days 7 to 15)
- Placebo (matched to moxifloxacin and CBP-307)
- Moxifloxacin (400 mg)

Moxifloxacin will be used as a positive control to determine the assay sensitivity of this study with an expected peak QT effect (placebo-corrected change-from-baseline QTcF; $\Delta\Delta QTcF$) of 10 to 15 msec.

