For the repeated-dose administration of CBP-307, the C_{max} and AUCs increased with the higher administered dose (Table 2). At the steady-state timepoint on Day 28, the median CBP-307 t_{max} was 4 to 6 hours. The average $t_{1/2}$ was similar, ranging 44 to 49 hours, and there were no dose-dependent changes in $t_{1/2}$ within the dose range. The $t_{1/2}$ was slightly prolonged after repeated-dose administration when compared with that after a single-dose administration. Moderate accumulation of CBP-307 (approximately 3 times the levels

following a single dose) was noted in plasma after QD administration for 14 consecutive days.

Table 2: Pharmacokinetics Parameters in the Multiple-Dose CBP-307 Regimen (Study CBP-307AU001)

Multiple-Dose Regimen PK Parameters	Multiple-Dose Cohort 1 CBP-307 Dosing, mg (\pm SD) (n)		Multiple-Dose Cohort 2 CBP-307 Dosing, mg (\pm SD) (n)	
	Day 1 0.1	Day 28 0.25	Day 1 0.15	Day 28 0.15
AUC ₀₋₂₄ (ng*h/mL)	24.5 \pm 3.26 (n = 5)	125 \pm 12.4 (n = 4)	26.3 \pm 7.45 (n = 5)	79.7 \pm 27.3 (n = 6)
AUC _{last} (ng*h/mL)	NA	203 \pm 21.9 (n = 4)	NA	131 \pm 44.7 (n = 6)
C _{max} (ng/mL)	1.45 \pm 0.214 (n = 5)	6.30 \pm 0.588 (n = 4)	1.32 \pm 0.422 (n = 6)	4.23 \pm 1.45 (n = 6)
t _{max} (hours)	6.80 \pm 1.50 (n = 5)	6.50 \pm 1.50 (n = 4)	5.00 \pm 0.68 (n = 6)	4.33 \pm 0.33 (n = 6)

Abbreviations: AUC₀₋₂₄ = area under the curve from time 0 to 24 hours; AUC_{last} = area under the curve at the last time point; C_{max} = maximum concentration; mg = milligram(s); NA = not applicable; ng/mL = nanogram(s) per milliliter; PK = pharmacokinetic; SD = standard deviation; T_{max} = time to maximum concentration.

Source: Final report for Study CBP-307AU001.

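### The accumulation ratio in Section 8.4 needs a Day 7 PK profile that is not scheduled, and adding one would still understate accumulation

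*Protocol*

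**What the plan says.** Section 8.4 lists the accumulation ratio among the PK parameters, for Cmax and for AUC0-24, "calculated as Day 15 C_{max} /Day 7 C_{max} and Day 15 AUC_{0-24} /Day 7 AUC_{0-24".

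Appendix 6, footnote 7, places the profiles (predose and nine times from 0.5 to 24 hours) "on each PK sampling day (Days 1, 6, 15, and 16". It adds only this: "Additional PK samples will be collected at 72 and 96 hours following dosing on Day 15". Section 3.1 gives the same days. In the schedule grid Day 7 lies in the column for Days 7 to 14, which has no PK mark. The extra activity on Day 7 is telemetry, which runs "until approximately 12 hours postdose on Days 1, 2, 3, and 7 (up-titration days".

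On dosing, the Synopsis gives "Starting doses of CBP-307 for titration (0.05 mg on Day 1 followed by an up-titrated dose of 0.1 mg on Day 2", then 0.2 mg on Days 3 to 6 and 0.5 mg on Days 7 to 15. Section 1.2.1.2 gives a half-life of about 25 hours after a single dose and, after repeated dosing, an average "ranging 44 to 49 hours". It also reports accumulation of about three times after 14 days of once-daily dosing.

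**The concern.** The protocol fixes both a formula and a sampling schedule, and the second does not supply what the first needs. This is not a detail left to the statistical analysis plan, because no data-handling rule can create a Day 7 Cmax or AUC0-24. The only draw near that time is the 24-hour sample of Day 6, in effect the trough before the first 0.5 mg dose.

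There is a second difficulty if the gap is closed simply by sampling on Day 7. A denominator for accumulation is normally the exposure from a first dose alone. Day 7 is the first 0.5 mg dose, but it is given on top of six earlier active doses. At stake is one planned PK descriptor, which will be missing for everyone, or biased low if rescued in the obvious way.

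**Working it through.** **Availability (no model needed).** Required: Cmax and AUC0-24 on Days 7 and 15. Scheduled: Days 1, 6, 15 and 16, plus two late samples. Day 7 is absent, so 0 of 32 Group 1 subjects are evaluable.

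The blood-volume table in Appendix 3 agrees. Its row "CBP-307/Moxifloxacin Pharmacokinetics (includes discard volume per draw") allows 41 draws of 8 mL, or 328 mL. Four days of 10 samples, plus 2 late samples, minus 1 draw shared between Day 15 at 24 hours and Day 16 predose, is 40 + 2 - 1 = 41. None is left for Day 7.

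**Which half-life fits the protocol's own accumulation figure.** Let r = 2^(-24/t½). Accumulation over 14 doses is (1 - r^14)/(1 - r).

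- t½ 44 to 49 h: 3.16 to 3.44.
- t½ 25 h: 2.06.
- Table 2, 0.15 mg, Day 28 over Day 1: 79.7/26.3 = 3.03 (AUC0-24) and 4.23/1.32 = 3.20 (Cmax).

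The stated factor of about three is reproduced by the repeated-dose half-life, not by the single-dose one.

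**What a Day 7 denominator would contain.** By linear superposition, relative exposure on day d is the sum of dose_j × r^(d-j), with doses 0.05, 0.1, 0.2 (four times) and 0.5 (nine times).

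At t½ 46.5 h (midpoint of 44 to 49), r = 0.699:

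- Earlier doses on Day 7: 0.2(r + r² + r³ + r⁴) + 0.1r⁵ + 0.05r⁶ = 0.376.
- Carry-over share: 0.376/(0.376 + 0.5) = 42.9%.
- Day 15: 0.5(1 - r⁹)/(1 - r) + 0.376r⁸ = 1.617.
- Day 15/Day 7: 1.617/0.876 = 1.85.
- Day 15 over one clean 0.5 mg dose: 1.617/0.5 = 3.2.

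| Assumption | Carry-over | Day 15/Day 7 | Day 15/one clean 0.5 mg dose |
|---|---|---|---|
| Proportional, 44 h | 41.8% | 1.81 | 3.11 |
| Proportional, 46.5 h | 42.9% | 1.85 | 3.24 |
| Proportional, 49 h | 44.0% | 1.88 | 3.36 |
| Proportional, 25 h | 28.7% | 1.46 | 2.05 |

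A one-compartment oral model with tmax 4 to 6 hours and t½ 44 to 49 hours gives 42.5 to 44.9% for Cmax and 43.0 to 45.9% for AUC0-24, close to the simple calculation.

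**Departure from proportionality.** In Table 1, AUCinf per mg is 63.7/0.25 = 255 at 0.25 mg and 214/0.5 = 428 at 0.5 mg fasted, a ratio of about 0.6 (n = 3 in each). Weighting the earlier doses by 0.6 at 46.5 h gives 0.6 × 0.376 = 0.226 and a carry-over of 0.226/0.726 = 31%. The Day 15/Day 7 ratio is then about (1.596 + 0.226r⁸)/0.726 = 2.2.

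**The case against.** Section 8.4 says the parameters are calculated where possible. That covers a subject with missing samples. It does not cover a parameter that no subject can have.

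Day 7 sampling could be added. Nine postdose draws of 8 mL add 72 mL, taking the total from 390.5 to 462.5 mL, under the 500 mL limit in Appendix 3. This stands as a matter of blood volume, but it leaves the carry-over.

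A reader might infer that about 43% carry-over is an established figure. It is not. It needs dose-proportional kinetics and the 44 to 49 hour half-life; other readings of the protocol's own data give about 29 or 31%.

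A reader might also infer that a Day 15/Day 7 ratio would not measure accumulation at all. That is too strong. It would describe the rise from the first to the ninth 0.5 mg dose, while understating accumulation relative to a single dose.

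Finally, a reader might infer harm to the QT conclusion or to bridging towards therapeutic steady state. The documents do not support either. The primary analysis in Section 8.3 uses Cmax on Days 6 and 15, the ratio is not among the endpoints named in Section 2.2.2, and no decision in the protocol rests on it.

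**Conclusion.** The contradiction between Section 8.4 and Appendix 6 is certain and needs no assumption: as defined, the accumulation ratio is unobtainable in every Group 1 subject.

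The further point, that Day 7 sampling would not fully repair it, depends on superposition. Under the assumptions tried, roughly 29 to 44% of Day 7 exposure would come from earlier doses. The upper part of that range rests on proportional kinetics with the half-life that best fits the reported threefold accumulation. The direction is the same throughout: the ratio would be too low as a measure of accumulation from a single dose. The consequence is confined to one secondary PK descriptor.

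**What to change.** Reconcile Section 8.4 with the sampling schedule in one of two ways.

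1. Delete the Day 15/Day 7 ratio.
2. Replace it with a value labelled as predicted, R_ac = 1/(1 - exp(-24 × lambda_z)), with lambda_z estimated from the washout after the Day 15 dose out to 96 hours. At 46.5 hours this gives 3.32, the steady-state limit, slightly above the 3.24 for Day 15.

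If the second is chosen, state that it assumes linear, time-invariant, mono-exponential kinetics (Section 1.2.1.2 reports a longer half-life after repeated dosing), and that it gives one value, not separate Cmax and AUC ratios. It is also valid only if no CBP-307 is given on Day 16. Table 3 in Section 5.1 shows none for Group 1 on that day, but the CBP-307/placebo administration row runs to Day 16 in one copy of the Appendix 6 schedule and stops at Day 15 in another. These must be reconciled.

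Day 1 is not a ready substitute denominator. Only placebo precedes it, but its dose is 0.05 mg, so dose normalisation would require the proportionality that Table 1 calls into question.

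Either option costs only wording in Section 8.4 and the analysis plan, with no extra sampling.

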8.5. Safety Analysis

All AEs will be listed and treatment-emergent AEs will be summarized using the descriptive methodology. Each AE will be coded using the Medical Dictionary for Regulatory Activities. Observed values for clinical laboratory test data, 12-lead ECGs, vital signs, and physical examination findings will be listed.

8.6. Interim Analysis

No interim analyses are planned for this study.

10. APPENDICES

Appendix 1: Adverse Event Reporting

Definitions

An AE is any untoward medical occurrence in a subject or clinical investigation subject administered a pharmaceutical product, which does not necessarily have a causal relationship with this treatment. An AE can therefore be any unfavorable and/or unintended sign (including a clinically significant abnormal laboratory finding), symptom, or disease temporally associated with the use of a study treatment, whether or not related to the study treatment. This includes any newly occurring event or previous condition that had increased in severity or frequency since the administration of study medication.

Examples of AEs include:

- Symptoms described by the subject, or signs observed by the investigator, and
- Abnormal findings (involving clinically significant abnormal laboratory tests, ECG, etc.)
- Exacerbation of previous condition, including increased incidence and/or severity.

Note: Regarding decreased lymphocyte count in peripheral blood in this study, please report them as follows:

- Since a decreased lymphocyte count in peripheral blood is due to the mechanism of action of the drug, it is not to be reported as an AE. However, clinical diagnosis related to a decreased lymphocyte count in peripheral blood indicates AE reporting (if no diagnosis is available, it is required to report related clinical symptoms or signs).

The investigator is to report all directly observed AEs and all AEs spontaneously reported by the study subject. In addition, each study subject will be questioned about AEs. All AEs will be recorded in the medical records and eCRFs. The investigator (or designee) is to record in detail any AE that occurred to the subject, including: AE diagnosis whenever possible, or signs, symptoms, the start date and time of occurrence, the stop date and time of occurrence, seriousness (ie, whether it is an SAE), severity of AEs, causality assessment, actions taken on the investigational product, other actions (eg, medications/treatments given), and outcomes of AEs.

Assessment of Severity

The investigator will be asked to provide an assessment of the severity of the AE using the following categories:

- **Mild:** Usually transient and may require only minimal treatment or therapeutic intervention. The event does not generally interfere with usual activities of daily living.
- **Moderate:** Usually alleviated with additional specific therapeutic intervention. The event interferes with usual activities of daily living, causing discomfort but poses no significant or permanent risk of harm to the subject.

- **Severe:** Interrupts usual activities of daily living, or significantly affects clinical status, or may require intensive therapeutic intervention.

Relationship to Study Treatment

The investigator (or designee) will make a determination of the relationship of the AE to the study treatment using a 4-category system according to the following guidelines:

- **Not Related:** The AE is definitely caused by the subject's clinical state or the study procedure/conditions.
- **Unlikely Related:** The temporal association between the AE and the drug is such that the drug is not likely to have any reasonable association with the AE.
- **Possibly Related:** The AE follows a reasonable temporal sequence from the time of drug administration but could have been produced by the subject's clinical state or the study procedures/conditions.
- **Related:** The AE follows a reasonable temporal sequence from the administration of the drug, abates upon discontinuation of the drug, follows a known or hypothesized cause-effect relationship, and (if appropriate) reappears when the drug is reintroduced.

Follow-up of Adverse Events

Every reasonable effort will be made to follow up with subjects who have AEs. Any subject who has an ongoing AE that is possibly related or related to the IMP or study procedures at the follow-up visit will be followed up, where possible, until resolution or until the unresolved AE is judged by the investigator (or designee) to have stabilized. This will be completed at the investigator's (or designee's) discretion. Any subject who has an ongoing AE that is not related or unlikely related to the IMP or study procedures at the follow-up visit can be closed out as ongoing at the investigator's discretion.

Adverse Drug Reactions

All noxious and unintended responses to an IMP (ie, where a causal relationship between an IMP and an AE is at least a reasonable possibility) related to any dose should be considered adverse drug reactions.

For marketed medicinal products, a response to a drug that is noxious and unintended and which occurs at doses normally used in man for prophylaxis, diagnosis, or therapy of diseases or modification of physiological function is to be considered an adverse drug reaction.

An unexpected adverse drug reaction is defined as an adverse reaction, the nature or severity of which is not consistent with the applicable product information (eg, IB for an unapproved IMP).

Serious Adverse Events

All SAEs will be collected after subjects sign the informed consent form and throughout the entire study, ie, until the end-of-study as specified in the protocol (or at early termination).

An SAE is defined as any untoward medical occurrence that at any dose either:

- results in death
- is life-threatening
- requires inpatient hospitalization or prolongation of existing hospitalization
- results in persistent or significant disability/incapacity (disability is defined as a substantial disruption of a person's ability to conduct normal life functions)
- results in a congenital anomaly/birth defect
- results in an important medical event (see below).

Important medical events that may not result in death, be life-threatening, or require hospitalization may be considered SAEs when, based upon appropriate medical judgment, they may jeopardize the subject and may require medical or surgical intervention to prevent one of the outcomes listed in this definition.

Instances of death or congenital abnormality, if brought to the attention of the investigator at any time after cessation of the study treatment and considered by the investigator to be possibly related to the study treatment, will be reported to the sponsor (or designee).

Definition of Life-threatening

An AE is life-threatening if the subject was at immediate risk of death from the event as it occurred (ie, does not include a reaction that might have caused death if it had occurred in a more serious form). For instance, drug-induced hepatitis that resolved without evidence of hepatic failure would not be considered life-threatening even though drug-induced hepatitis can be fatal.

Definition of Hospitalization

Adverse events requiring hospitalization should be considered serious. In general, hospitalization signifies that the subject has been detained (usually involving an overnight stay) at the hospital or emergency ward for observation and/or treatment that would not have been appropriate at the study site. When in doubt as to whether hospitalization occurred or was necessary, the AE should be considered as serious.

Hospitalization for elective surgery or routine clinical procedures, which are not the result of an AE, need not be considered AEs and should be recorded on a clinical assessment form and added to the eCRF. If anything untoward is reported during the procedure, this must be reported as an AE and either 'serious' or 'nonserious' attributed according to the usual criteria.

Serious Adverse Event Reporting

The investigator will complete an SAE report form and forward it by facsimile or email to Labcorp APAC Drug Safety and the sponsor immediately (within 24 hours) upon becoming aware of an SAE.

All SAEs must be reported immediately (within 24 hours of discovery) to: [contact]

SAE Reporting email: [contact] (preferred method)

Labcorp Safety SAE Reporting [contact] or [name] (toll free)

The responsibilities of Labcorp APAC Drug Safety include the following:

- Prepare an AE reporting plan prior to the start of the study. Where this plan differs from the applicable study site standard operating procedure on SAE reporting, the safety management plan will always take precedence.
- Receive and review SAE report forms from the study site and inform the sponsor of the SAE within 1 working day of the initial notification to Labcorp APAC Drug Safety who will delete any information from the SAE report forms that may identify the subject.
- Write case narratives and enter the case into Labcorp's safety database as defined in the AE reporting plan.
- Produce appropriate reports of all suspected unexpected serious adverse reactions and forward them to the EC, Medicines and Healthcare Products Regulatory Agency, principal investigator, and the sponsor within the timeframes stipulated in the Clinical Trials Directive Guideline (ENTR/CT 3).

The responsibility for reporting SAEs will be transferred to the sponsor 28 days after the end of the study.

For SAEs, the active reporting period to sponsor or its designated representative begins from the time that the subject provides informed consent through to the last subject visit.

Nonserious AEs should be collected from the time the subject has taken the placebo dose on Day -1 through the last subject visit. If AEs that occur in the screening prior to the placebo administration to all subjects on Day -1 are considered to be related to the study procedure, they should be also collected.

The investigator is to report all directly observed AEs and all AEs spontaneously reported by the study subject. In addition, each study subject will be questioned about AEs.

Each AE is to be assessed to determine if it meets the criteria for SAEs. If an SAE occurs, the sponsor should be notified within 24 hours of investigator awareness of the event. This time frame also applies to additional new information (follow-up) on previously forwarded SAE reports as well as to the initial and follow-up reporting of exposure during pregnancy.

In the rare event that the investigator does not become aware of the occurrence of an SAE immediately (eg, if an outpatient study subject initially seeks treatment elsewhere), the investigator is to report the event within 24 hours after learning of it and document the time of his or her first awareness of the AE.

For all SAEs, the investigator is obligated to pursue and provide information to the sponsor in accordance with the time frames for reporting as specified above. In addition, an investigator

may be requested by the sponsor to obtain specific additional follow-up information in an expedited fashion. This information collected for SAEs is more detailed than that captured on the AE eCRF. In general, this will include a description of the AE in sufficient detail to allow for a complete medical assessment of the case and independent determination of possible causality. Information on other possible causes of the event, such as concomitant medications, vaccines, and/or illnesses, must be provided. In the case of a subject death, a summary of available autopsy findings must be submitted as soon as possible to the sponsor or its designated representative.

Pregnancy

Pregnancy (maternal or paternal exposure to study treatment) does not meet the definition of an AE. However, to fulfill regulatory requirements any pregnancy should be reported following the SAE process to collect data on the outcome for both mother and fetus.

If the female subject becomes pregnant during the clinical trial and has not yet been dosed with study treatment, she must be withdrawn from the study. If the female subject becomes pregnant during the clinical trial and has been dosed, she must discontinue treatment immediately but may remain on study for safety evaluations. If the partner of a male subject becomes pregnant during the clinical trial, the subject can continue the clinical trial.

For pregnancy of female subjects or partners of the male subjects during this study, investigators should report to the sponsor or designee in a pregnancy report form within 24 hours after investigator awareness and report to the EC in time as per local requirement.

The investigator will follow up on pregnancy outcomes, until not less than 12 months after birth, unless otherwise justified, and will report the outcome to the sponsor and ethics committee.

If any adverse pregnancy outcome (eg, the outcome of the pregnancy is stillbirth, spontaneous abortion, or fetal malformations), it should be considered as an SAE and be reported in accordance with SAE reporting requirements.

